Internet-delivered Cognitive Behavior Therapy Compared to Stress Management for Atrial Fibrillation- a Randomized Controlled Trial With Active Control

Version 1. 2023-03-03. Established

Version 2. 2023-03-28. Changed title to match Clinical trials registration. Added logo.

This is analysis plan for the study approved by the Regional Ethics Committee in Stockholm on February 26, 2022 (reg no 2020-00197).

Clinical trials registration completed on June 24, 2021. Last update published on September 1, 2022.

ID: No: NCT04962932

Principal Investigator:

[name],

Department of Clinical Neuroscience, Division of Psychology

[name]

Karolinska Institutet, Stockholm, Sweden

Email: [contact],

[contact]

Statistical Analysis Plan

The primary outcome of the study is the difference between the treatment groups in AFEQT quality of life measured on a scale ranging from zero (severe symptoms and disability) to 100 (no symptoms and no disability). The patients are observed at baseline and again every week for twelve consecutive weeks. The difference between treatment groups in the mean quality of life score at twelve weeks is estimated with a linear mixed effect model. The quality-of-life score is the dependent variable.

The independent variables are a numeric time variable, a binary treatment indicator, and an interaction term between time and treatment. The model includes subject-specific random intercepts, which are assumed to follow a normal distribution. The random intercept can appropriately handle the potential temporal stochastic dependence in the data. The estimates for the parameter values are obtained by maximizing the corresponding likelihood function.

The linearity of the relationship between mean score and time assumed by the model is evaluated visually and tested formally by introducing restricted cubic splines for time in the model. Link functions are explored if necessary to ensure that the inferences on the mean are within the feasible bounded intervals of each outcome. The significance of each comparison is based on Wald's tests and deemed significant if below 5%.

Between group effect sizes are measured by the Cohen's d statistic, defined as the ratio between the mean score difference at twelve weeks and the baseline standard deviation of the score variable. Standard errors and confidence intervals are estimated with 5,000 cluster-bootstrap samples.

All the secondary and exploratory outcomes are measured by numeric variables. They are analyzed with the same approach as the primary outcome. For the secondary outcomes (AFSS-visits, BSQ, SF-12, GSLTPAQ, ISI-5, PHQ-2, GAD-2, PCS) that have only two measurements over time (baseline and post-treatment) testing for departures from linearity is unfeasible.

The patterns and causes of possible missing values are investigated. The inflated statistical level resulting from the multiple comparisons is taken into account in the interpretation of the results and addressed in reports and manuscripts.

The main manuscript shows the results for the following secondary outcomes: SCL, CAQ, BSQ, SF-12, CSQ and AFFS-visits. The supplement shows the results for the following secondary outcomes: GSLTPAQ, PSS-4, PCS, ISI-5, PHQ-2 and GAD-2.

The measures of non-specific effects that are collected at week 2, Credibility Scale and Working Alliance Inventory are compared between the groups with the t-tests.

Adverse events are collected weekly and at post-treatment, at the latter timepoint with respect to the entire treatment period. The sum and mean severity rating of adverse events for each patient over the treatment period is compared between the groups with the t-test and the Mann-Whitney's U test, respectively. The incidence and severity rating of adverse events at post-treatment will be compared using t-test and Mann-Whitney U test, respectively.

Changes from post-treatment to six-month follow-up will be compared within each group only. No between-groups test will be performed on six-month data because the study was not powered to detect potential differences between the groups six months after treatment completion.

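### The week-12 difference and the Cohen's d built on it are not adjusted for the baseline score, which costs precision and lets chance baseline imbalance pass in part into the estimate

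*SAP*

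**What the plan says.** All of this is in the section headed Statistical Analysis Plan.

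- **Target.** "The difference between treatment groups in the mean quality of life score at twelve weeks is estimated with a linear mixed effect model".
- **Schedule and response.** "The patients are observed at baseline and again every week for twelve consecutive weeks", and "The quality-of-life score is the dependent variable". The SAP does not say outright that the baseline score is a response row. The schedule implies it, and so does the remark on secondary outcomes "that have only two measurements over time (baseline and post-treatment) testing for departures from linearity is unfeasible", which counts baseline as one of the measurements over time.
- **Fixed effects.** "The independent variables are a numeric time variable, a binary treatment indicator, and an interaction term between time and treatment".
- **Random effects.** "The model includes subject-specific random intercepts, which are assumed to follow a normal distribution".
- **Effect size.** Cohen's d is "defined as the ratio between the mean score difference at twelve weeks and the baseline standard deviation of the score variable".
- **Secondary and exploratory outcomes.** "They are analyzed with the same approach as the primary outcome". Eight of them have only a baseline and a post-treatment score.

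The SAP nowhere mentions a baseline covariate, a common baseline mean or any other baseline adjustment.

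**The concern.** With these terms the week-12 difference is the treatment coefficient plus 12 times the interaction coefficient. The treatment coefficient is the freely estimated group difference at time 0, so a chance difference at baseline is carried into the contrast.

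The random intercept does not prevent this. With complete data the estimate equals the difference between two straight lines fitted separately to the arms. The random intercept changes the standard error but does not condition the contrast on the baseline score.

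The baseline score is collected anyway. Leaving it out of the contrast gives wider confidence intervals and less power than the same data allow. Given an observed imbalance, part of it also shows up in the reported difference and in d. These are two views of one loss: averaged over randomisations, the pass-through is already contained in the larger variance.

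**Working it through.** **Inputs.** From the SAP: 13 occasions (weeks 0 to 12), linear time, random intercept, week-12 contrast. Assumed, because the SAP gives no values: within-patient correlation ρ of 0.3 to 0.8, complete data, total variance 1, and 40 to 100 patients per arm. Variances below are in units of 2/n, with n per arm. The SAP states no power or precision figure, so there is none to reproduce.

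**1. Planned contrast.** For weeks 0 to 12 the mean time is 6 and the sum of squares is 182. The residual part at week 12 is 1/13 + 6²/182 = 0.275.

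Variance = ρ + 0.275(1 − ρ).

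**2. Baseline as covariate, linear time on weeks 1 to 12.** The mean time is 6.5 and the sum of squares is 143. The residual part is 1/12 + 5.5²/143 = 0.295. Adjustment reduces the between-patient part from ρ to ρ − ρ².

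Variance = ρ − ρ² + 0.295(1 − ρ).

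| ρ | Planned | Adjusted | Adjusted / planned |
|---|---|---|---|
| 0.3 | 0.492 | 0.416 | 0.85 |
| 0.5 | 0.637 | 0.397 | 0.62 |
| 0.7 | 0.782 | 0.298 | 0.38 |

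Simulation (6,000 trials per setting, 40 and 60 per arm) gave 0.86/0.85, 0.64/0.61 and 0.37/0.39.

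The result does not hinge on whether baseline is a response row. If the planned model used weeks 1 to 12 only, its variance would be ρ + 0.295(1 − ρ) = 0.506, 0.647 and 0.788. The ratios would then be 0.82, 0.61 and 0.38.

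**3. Pass-through of baseline imbalance.** The baseline observation has weight 1/13 + (12 − 6)(0 − 6)/182 = −0.121 in the planned contrast. The expected shift per unit of baseline difference is therefore ρ − 0.121(1 − ρ) = 0.22, 0.44, 0.66 and 0.78 at ρ = 0.3, 0.5, 0.7 and 0.8. After adjustment it is 0 under this covariance.

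One standard error of the baseline difference is √(2/n) = 0.224 SD at 40 per arm and 0.141 SD at 100. Such an imbalance shifts the estimate by between 0.141 × 0.22 = 0.03 SD and 0.224 × 0.66 = 0.15 SD for ρ from 0.3 to 0.7.

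**4. Two-occasion outcomes.** With complete data the planned contrast is exactly the raw post-treatment difference (variance 1). The adjusted variance is 1 − ρ². The planned variance is 1/(1 − ρ²) = 1.10, 1.33 and 1.96 times the adjusted one at ρ = 0.3, 0.5 and 0.7.

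**5. Splines instead of linear time.** With restricted cubic splines (3 or 4 knots at assumed quantiles) under the same covariance, the ratios are 0.89 to 0.91, 0.68 to 0.71 and 0.43 to 0.46.

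**6. Correlation that decays over the weeks.** The true covariance here is autoregressive, some cases with 20% added noise, and the working random intercept is kept.

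| Week-to-week correlation | Added noise | Baseline to week-12 correlation | Ratio, plain covariate | Ratio, with baseline-by-time term |
|---|---|---|---|---|
| 0.98 | none | 0.78 | 0.42 | 0.41 |
| 0.98 | 20% | 0.63 | 0.57 | 0.56 |
| 0.95 | 20% | 0.43 | 0.84 | 0.81 |
| 0.93 | 20% | 0.33 | 0.94 | 0.90 |
| 0.90 | none | 0.28 | 1.03 | 0.95 |
| 0.90 | 20% | 0.23 | 1.03 | 0.96 |
| 0.80 | 20% | 0.06 | 1.10 | 1.02 |

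A plain covariate breaks even at a correlation near 0.3. In these cases it also leaves some negative pass-through, which the baseline-by-time term removes.

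**7. If the interaction alone were read as the effect.** The variance of 12 × interaction is (144/182)(1 − ρ) = 0.554, 0.396 and 0.237. That is 1.33, 1.00 and 0.80 times the adjusted variance at ρ = 0.3, 0.5 and 0.7. For two-occasion outcomes the corresponding ratio is 2/(1 + ρ) = 1.54, 1.33 and 1.18.

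**The case against.** The strongest reply is that the SAP's model is a valid analysis of its stated target, so this is a preference between two sound methods. That stands as a limit on severity: the point concerns efficiency and no validity claim is made.

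A second reply is that the size rests on assumptions. Neither ρ nor the sample size is in the SAP, and no shortfall against a planned power can be shown. That also stands. The ratios 0.85, 0.62 and 0.38 belong to the favourable setting of constant correlation and linear time. Splines or decaying correlation give smaller gains, but still gains unless baseline is only weakly related to week 12.

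Third, the SAP does not name the coefficient its Wald tests address. If the interaction were tested, the primary outcome would show no general gain. However, the SAP defines both the target and the numerator of d as the week-12 mean difference, so this reading is the less likely one. The two-occasion outcomes gain under either reading.

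Fourth, the SAP allows link functions to be explored. Under a nonlinear link a baseline covariate makes the treatment coefficient conditional on baseline, so the week-12 mean difference has to be recovered by averaging over baseline. This is real extra work, but routine.

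**Conclusion.** The concern holds. The planned week-12 difference is not adjusted for baseline, for the primary outcome or for any secondary outcome analysed the same way. It is unbiased under randomisation, and leaving out baseline does not inflate the type I error rate. The change is recommended, not essential to validity.

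Under the SAP's own covariance, an assumed ρ of 0.5 and linear time, the planned analysis needs about 1/0.62 = 1.6 times as many patients for the same precision, and it passes on 0.44 of a chance baseline difference. The case is clearest for the eight two-occasion outcomes, where the algebra needs no assumption about the shape of the time course.

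The absence of adjustment is certain from the text. The amount gained depends on the baseline to week-12 correlation. It is small or nil below about 0.3 with a plain covariate, and at worst about a 2% loss in the cases computed with a baseline-by-time term.

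**What to change.** - **Primary outcome.** Model the post-baseline scores with the baseline score as a covariate. Keep the planned time, treatment and interaction terms, linear or spline as the linearity check indicates. Include a baseline-by-time term to protect against decaying correlation.
- **Secondary outcomes.** Do the same wherever a baseline score exists. For two-occasion outcomes this is a regression of the post-treatment score on arm and baseline.
- **Effect size.** Take the numerator of d from the adjusted week-12 difference and keep the baseline SD as denominator. If a nonlinear link is used, average over baseline to obtain the mean difference.
- **What to avoid.** Do not switch to categorical week at the same time. Under the SAP's covariance the adjusted variance would then be 1 − ρ², which exceeds the planned ρ + 0.275(1 − ρ) when ρ is below about 0.56. Simply dropping the treatment main effect is also unsafe: with autoregressive data and a baseline to week-12 correlation of 0.3, it multiplies the variance by 1.26.

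**Cost.** A rewritten model sentence and a stated rule for missing baseline scores, with no new data. Patients without any post-baseline score no longer enter the model. Little is gained if baseline proves only weakly related to week 12.

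### Full maximum likelihood with Wald tests and no small-sample correction makes the week-12 comparison slightly too liberal if the usual normal reference is used

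*SAP*

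**What the plan says.** All references are to the unnumbered text under the heading Statistical Analysis Plan in the SAP.

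- **Contrast.** "The difference between treatment groups in the mean quality of life score at twelve weeks is estimated with a linear mixed effect model". Measurements: "The patients are observed at baseline and again every week for twelve consecutive weeks", so 13 per patient.
- **Model.** The fixed part has three terms, namely time as a number, arm, and their product. For the random part, where no random slope is named: "The model includes subject-specific random intercepts, which are assumed to follow a normal distribution".
- **Estimation.** "The estimates for the parameter values are obtained by maximizing the corresponding likelihood function".
- **Decision rule.** "The significance of each comparison is based on Wald's tests and deemed significant if below 5" per cent. Sidedness, reference distribution and degrees of freedom are not given.
- **Standard errors.** The only sentence on them closes the paragraph that defines Cohen's d: "Standard errors and confidence intervals are estimated with 5,000 cluster-bootstrap samples". Whether it covers only d, or the Wald tests as well, is not said.
- **Other outcomes.** Of the secondary and exploratory outcomes: "They are analyzed with the same approach as the primary outcome". Eight listed secondary outcomes have only a baseline and a post-treatment value.

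No number of patients appears in the SAP.

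**The concern.** Full maximum likelihood takes no account of the fixed effects when it estimates variances. With two arms and N patients it divides the between-patient sum of squares by N, although only N − 2 degrees of freedom are available, so the variance and the standard error come out slightly low. A Wald ratio referred to the normal distribution then treats that estimate as if it were known. Both steps lower the p-value. Neither depends on missing data or on a wrong covariance model, so the point is separate from whether a random intercept alone is adequate.

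At stake is whether the 5% rule delivers 5%. The departure favours declaring a difference, touches the primary comparison, and recurs for each outcome analysed in the same way.

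**Working it through.** **Inputs.** From the SAP: 13 measurements at weeks 0 to 12 (primary), 2 measurements (eight secondary outcomes), random intercept only, maximum likelihood, Wald test, 5%. Assumed: total N from 40 to 200, equal arms, complete data, two-sided test, normal reference (critical value 1.96), and an intraclass correlation of 0.5 to 0.7 for the weekly outcome. The SAP has no sample size or power figure to reproduce; its 5% is a chosen threshold.

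**Two-measurement outcomes, interaction term (exact).** The test rests on N within-patient changes in two groups. The ML variance is (N − 2)/N times the unbiased one, so

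actual level = 2 × P( t with N − 2 df > 1.96 × √((N − 2)/N) ).

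For N = 40: √(38/40) = 0.975, 1.96 × 0.975 = 1.910, and 2 × P(t with 38 df > 1.910) = 6.4%.

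| Total N | ML SE ÷ unbiased SE | ML, normal | REML, normal | REML, t |
|---|---|---|---|---|
| 40 | 0.975 | 6.4% | 5.7% | 5.0% |
| 60 | 0.983 | 5.9% | 5.5% | 5.0% |
| 100 | 0.990 | 5.5% | 5.3% | 5.0% |
| 200 | 0.995 | 5.3% | 5.1% | 5.0% |

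Roughly half of the excess comes from the ML divisor and half from the normal reference. REML alone would not restore 5%.

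**Weekly outcome, week-12 difference (simulation).** Mean time is week 6 and the sum of squared centred times is 182. The contrast is the arm difference in patient mean plus 6 times the arm difference in slope. Its variance is

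(4/N) × [ B/13 + 36 × W/182 ],

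with B the between-patient mean square and W the within-patient residual variance. ML uses B = SSB/N and W = SSW/(12N); REML uses SSB/(N − 2) and SSW/(12N − 2).

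At intraclass correlation 0.6 and total variance 1, W = 0.4 and B = 0.4 + 13 × 0.6 = 8.2. The two terms are 8.2/13 = 0.631 and 36 × 0.4/182 = 0.079, so 0.631/0.710 = 89% of the variance comes from the part with only N − 2 degrees of freedom. This is why the week-12 contrast is affected.

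| Total N | ML, normal (400,000 draws) | Separate run (40,000 draws) | Bootstrap analogue, normal |
|---|---|---|---|
| 40 | 6.1% | 6.0% | 6.3% |
| 60 | 5.7% | 5.9% | 6.1% |
| 100 | 5.4% | 5.5% | 5.5% |
| 200 | 5.2% | 5.1% | 5.2% |

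Monte Carlo error in the 40,000-draw columns is about 0.11 points. REML with t on N − 2 degrees of freedom gives 4.8–5.0%. The bootstrap analogue uses the variance of each patient's fitted week-12 value with divisor n per arm, so it shares the too-large divisor.

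**Weekly slope term alone (exact).** Same formula with 12N − 2 degrees of freedom: 5.1% at N = 40 and 5.0% from N = 100.

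**The case against.** The strongest case against is that nothing in the SAP is wrong. Maximum likelihood with Wald tests is a standard large-sample analysis, and a p-value threshold of 5% is not a promise of exact finite-sample size. The normal reference is inferred, since the SAP names none, and much of the excess depends on it. All of this stands, and it limits the point to a refinement.

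Second, a reader might infer that the tests use maximum-likelihood standard errors. The SAP does not say so: its one sentence on standard errors names the cluster bootstrap. Its position after the definition of Cohen's d suggests that it concerns d, but the wider reading is open. On that reading the mechanism changes, while the excess stays about the same.

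Third, switching every test to model-based REML could do harm. If patients' slopes vary and the random-intercept model ignores this, the model-based week-12 test reached about 7% to 11% with 60 to 120 patients (assumed slope SD 0.03 to 0.06 of the total SD per week). REML did not correct that, whereas the bootstrap analogue stayed near 5.5% to 6%. This objection stands and shapes the fix.

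Finally, the SAP already says that multiple comparisons are considered in interpretation, so a few tenths of a point on a secondary outcome are unlikely to change a conclusion.

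**Conclusion.** The point holds as a minor one. With a normal reference, the week-12 test exceeds 5% by about 1.1 points at 40 patients in total, 0.7 at 60, 0.4 at 100 and 0.2 at 200. For the two-measurement interaction the excess is 1.4, 0.9, 0.5 and 0.3 points. These figures assume equal arms, complete data, a true random-intercept model and a two-sided test.

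Three stronger readings are tempting and not supported:

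- **That the trial is small.** The SAP gives no N, so the upper end of the range cannot be attributed to this trial.
- **That every mixed-model test is affected.** The slope term of a weekly outcome is practically at 5%.
- **That the standard error is about 4% too small at 40 patients.** That figure arises only for two-measurement outcomes with 30% missing at post-treatment and an assumed correlation of 0.5. With complete two-measurement data the shortfall is 2.5% at 40 and 1.0% at 100.

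**What to change.** State which standard error and which reference distribution the Wald tests use, then apply one of two wordings, for the primary outcome and for all outcomes analysed in the same way.

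- **If tests and intervals are model-based:** estimate by REML and use a t reference with Kenward-Roger or Satterthwaite degrees of freedom. Keep full maximum likelihood only for likelihood-ratio comparisons of mean structures, such as a spline check of linearity.
- **If the 5,000-sample cluster bootstrap is meant to supply standard errors for the tests as well as for Cohen's d:** say so, keep it, and refer the Wald ratio to a t distribution with about (patients minus 2) degrees of freedom. Do not replace it with purely model-based standard errors. A little excess remains because of the divisor. With the t critical value of 2.024 at N = 40, 2.024 × 0.975 = 1.973 and 2 × P(t with 38 df > 1.973) = 5.6%; the same step gives 5.2% at N = 100.

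The SAP also allows link functions. REML with these degrees of freedom does not carry over to them directly, so name the reference distribution for that case too.

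The cost is a sentence or two of SAP text and a software setting. The only downside is that p-values become very slightly larger.

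### The weekly adverse-event sum is compared by t-test without allowing for how much of the treatment period each patient's reports cover (minor)

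*SAP*

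**What the plan says.** All relevant text is in the SAP's single Statistical Analysis Plan section.

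- Collection: "Adverse events are collected weekly and at post-treatment, at the latter timepoint with respect to the entire treatment period". The recall window is given for the post-treatment report only, not for the weekly one.
- Weekly data: "The sum and mean severity rating of adverse events for each patient over the treatment period is compared between the groups". Two tests are then named in the same order, so the sum is tested by t-test and the mean severity by Mann-Whitney.
- Post-treatment data: "The incidence and severity rating of adverse events at post-treatment will be compared using t-test and Mann-Whitney U test, respectively".
- Missing data: "The patterns and causes of possible missing values are investigated". No rule follows for adverse events.
- Schedule, stated for the primary outcome: "The patients are observed at baseline and again every week for twelve consecutive weeks".

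The mixed model is specified for the primary, secondary and exploratory outcomes. Adverse events have their own tests.

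**The concern.** A raw sum mixes two things: how often events occur, and how much of the treatment period the patient reported on. A patient who stops reporting in week 6 contributes no events after that week, whatever happened. The same applies to a skipped week, unless a later report asks about it.

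If coverage is the same in both arms, both sums shrink alike and the comparison is fair. If it differs, the arm with less coverage looks safer than it is. In a safety comparison the more serious consequence is the reverse side of this: a real excess of events in the arm with more dropout is shrunk or cancelled. The choice of summary and test is written into the SAP, so this is not a detail left to the protocol. The primary outcome is not affected.

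**Working it through.** The SAP has no figure to reproduce here. It gives no sample size, event rate or completion rate.

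**Inputs**
- From the SAP: weekly collection, raw sum, t-test.
- Assumed: 12 weekly reports (the SAP states the 12-week schedule for the primary outcome); two-sided 5% level (the SAP states 5% for Wald tests); 60 patients per arm; 0.1, 0.4 or 0.6 events per week; the coverage levels below; 'sum' read as a count.

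**Step 1: expected sums.** Expected sum = weekly rate × 12 × coverage. At equal true rates the ratio of sums is therefore the ratio of coverage.
- 90% v 85%: 0.85/0.90 = 0.944, 6% fewer events.
- 90% v 80%: 0.80/0.90 = 0.889, 11% fewer. At 0.5 per week this is 5.4 v 4.8 events.
- 90% v 70%: 0.70/0.90 = 0.778, 22% fewer, or 5.4 v 4.2 events.

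This ratio holds equally if 'sum' means summed severity ratings.

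**Step 2: true excess that is fully cancelled.** 0.90/0.85 − 1 = 5.9%; 0.90/0.80 − 1 = 12.5%; 0.90/0.70 − 1 = 28.6%.

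**Step 3: false-positive rate.** Simulation with 10,000 trials per setting: patient rates gamma (shape 1 or 3), completed reports binomial(12, coverage), events Poisson, each report asking about one week only. Percentage of trials in which the raw-sum t-test rejects at equal true rates, for 0.1, 0.4 and 0.6 events per week:

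| Coverage | Shape 1 | Shape 3 |
|---|---|---|
| 90 v 90 | 4.8, 5.1, 4.5 | 5.2, 4.5, 5.1 |
| 90 v 85 | 5.5, 5.6, 5.5 | 6.0, 7.0, 7.3 |
| 90 v 80 | 7.5, 8.4, 8.4 | 8.5, 13.9, 14.3 |
| 90 v 70 | 14.9, 22.1, 22.9 | 20.8, 40.7, 46.3 |

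Events per week covered (here the same as per completed report): 4.5%–5.2% in all 24 settings.

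**Step 4: early stopping.** If 20% v 40% stop at a random week (coverage 89% v 78%), the raw sum rejects in 7.1%–14.4%. At 20% v 60% (89% v 67%) it rejects in 16.7%–43.0%. Per week covered: 4.6%–5.1%.

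**Step 5: masking.** If the arm with less coverage has a true rate 50% higher, the raw sum detects it in 21%–60% of trials at 90% v 80%, against 35%–89% per week covered. At 90% v 70% the figures are 8%–21% against 34%–88%.

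**Step 6: if each report asks about the time since the last one.** Skipped weeks are then captured later. The raw sum rejects in about 5%, but events per *completed report* rejects in 7%–15% (90% v 80%) or 15%–47% (90% v 70%), now against the arm that reports less. The count of reports is then the wrong denominator; the weeks those reports cover is the right one.

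**The case against.** The strongest objection is that the SAP does not say what period a weekly report covers. A reader might infer that every missed week adds nothing to the sum, and so that dividing by completed reports is the remedy. The document supports neither. If the form asks about the time since the last report, a skipped week loses little, the raw sum is sound for patients who keep reporting, and dividing by reports creates the bias it was meant to remove (Step 6). This objection stands and determines the form of the fix. It does not help with patients who stop reporting altogether, whose later weeks are lost under either window.

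Second, the SAP plans a separate comparison of a post-treatment report on the whole period, which does not depend on the weekly reports. If everyone attends and recalls fully, both analyses favour the arm reporting less in only 2.3%–2.7% of trials. This stands as a partial safeguard. It does not reach patients lost before post-treatment, and the SAP does not say how to read the two results if they disagree.

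Third, missing-value patterns are to be investigated, and completion by arm fits naturally under that. True, but an inspection does not change the test.

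Fourth, every magnitude is assumed, and nothing in the SAP suggests unequal reporting; its title describes an active control. At 90% v 85% the test is near nominal, and the 46% combines the widest coverage gap, the highest event rate and the less dispersed setting. This stands, and it limits the weight of the point.

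**Conclusion.** The point holds, with minor weight. The SAP fixes a raw sum with no allowance for coverage. If coverage differs between arms, the sum misstates the comparison in proportion to coverage: 11% at 90% v 80% and 22% at 90% v 70%. With equal coverage there is no such bias, and skipped weeks cause none if later reports capture them.

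The proportional figures follow from arithmetic once coverage is assumed and missed weeks are unrelated to events. The rejection rates also rest on the assumed sample size, event rates and count reading of 'sum'. A reader might go on to infer that the planned safety comparison is invalid, or that a false safety advantage is likely in this trial. The SAP supports neither: it has no data on coverage, and it has a second, whole-period measure.

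Two further gaps are separate clarifications and add no weight: whether 'sum' means a count or summed ratings, and whether patients without events enter the severity comparisons in the lowest category or are excluded.

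**What to change.** - State the recall window of the weekly report.
- Compare adverse events per week covered. If each report asks about the past week alone, weeks covered is the number of completed reports. If it asks about the time since the last report, it is the number of weeks up to the last report.
- Fix one method in advance: a t-test on the per-patient rate, which keeps the planned test, or a negative binomial model with log(weeks covered) as offset. Under the one-week window at 90% v 70%, the latter rejected in 4.4%–5.7% (1,000 trials per setting).
- Tabulate weeks covered by arm, count patients with no report by arm, and keep the raw sum as a supporting analysis.
- Say how the weekly and post-treatment results are read together.

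**Cost.** A few sentences, slightly more analysis and no new data. For a true 50% excess with 80% coverage in both arms, power is 35%–89% (rate) v 35%–87% (raw sum). With 40% stopping early in both arms it is 29%–84% v 30%–74%, the largest loss being 42% v 46% at 0.1 events per week. Patients with no report drop out of the rate: 1.7%, 3.3% and 5.0% of an arm when 20%, 40% and 60% stop at a random week. A t-test on rates also gives a patient with one covered week the same weight as one with twelve.

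**Remaining limit.** The rate is still biased if missing weeks are related to events. Example with a one-week window, 0.4 events per week in both arms, and the other arm at 90% at random: one arm reports 70% of event weeks and 85% of event-free weeks. P(event week) = 1 − exp(−0.4) = 0.330, so coverage = 0.330 × 0.70 + 0.670 × 0.85 = 0.80. The rate ratio is 0.70/0.80 = 0.87, 13% too low, against 0.70/0.90 = 0.78, 22% too low, for the raw sum.

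### Comparing each patient's mean adverse-event severity can favour an arm that only has extra mild events, and the mean does not exist for patients without an event

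*SAP*

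**What the plan says.** The adverse-event paragraph of the SAP describes two sources: "Adverse events are collected weekly and at post-treatment, at the latter timepoint with respect to the entire treatment period". For the weekly reports it forms two summaries per patient: "The sum and mean severity rating of adverse events for each patient over the treatment period is compared between the groups with the t-test". The sentence then assigns the tests in order ("is compared between the groups with the t-test and the Mann-Whitney's U test, respectively"), so the sum gets the t-test and the mean severity gets Mann-Whitney.

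For the post-treatment report it plans: "The incidence and severity rating of adverse events at post-treatment will be compared using t-test and Mann-Whitney U test, respectively".

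The paragraph does not give the denominator of the mean, the value for a patient without an event, or a rule for reading the two results together. The only general statement on missing data, "The patterns and causes of possible missing values are investigated", assigns no severity value to an event-free patient.

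**The concern.** A harm measure should not improve when harm is added. A mean over events does improve when the added events are milder than those the patient already has, because each mild event enlarges the denominator by more than its share of the numerator. Mann-Whitney then ranks that patient as better off.

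The second difficulty is that a patient with no event has no mean. Unless a value is assigned, the patient leaves the ranking. Having an event is an outcome after randomisation, so the patients who remain are no longer the randomised groups, and the share removed differs between arms whenever event rates differ.

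At stake is a reported finding of significantly lower severity in an arm whose only difference is additional events.

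**Working it through.** The SAP gives no sample size, event rate or severity scale for adverse events, so there is no planned figure to reproduce. The check is arithmetic, followed by simulation under stated assumptions.

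**One patient.** One event rated 3: mean = 3/1 = 3.00, sum of ratings = 3. Add five events rated 1: mean = (3 + 5×1)/6 = 8/6 = 1.33, sum of ratings = 8. The burden rises and the mean falls. With no event the mean is 0/0.

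**Assumptions (none from the SAP).** Both arms have Poisson background events with a mean of 1 or 2 per patient, rated 1/2/3 with probability 0.4/0.4/0.2. One arm has in addition a Poisson mean of 1 extra event per patient. There are 40, 60 or 100 patients per arm, tests are two-sided at 5%, and event-free patients are dropped.

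**Expected mean severity among patients with an event.**
- Background: 0.4×1 + 0.4×2 + 0.2×3 = 1.80.
- All added events rated 1: (1×1.80 + 1×1)/2 = 1.40 at background 1; (2×1.80 + 1×1)/3 = 1.53 at background 2.
- Added events rated 1/2/3 with probability 0.6/0.3/0.1 (mean 1.50): (1.80 + 1.50)/2 = 1.65 and (3.60 + 1.50)/3 = 1.70.
- Added events with the background mix: 1.80 in both arms.

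**Share of patients with no value.** At background 1: exp(−2) = 14% with the added events against exp(−1) = 37% without. At background 2: exp(−3) = 5% against exp(−2) = 14%.

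**Trials in which Mann-Whitney on the mean significantly favours the arm with added events** (ranges are over repeated sets of runs):

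| Ratings of added events | Background 1; 40 / 60 / 100 per arm | Background 2; 40 / 60 / 100 per arm |
|---|---|---|
| All rated 1 | 67% / 84–86% / 98% | 55–63% / 73–76% / 94–95% |
| 0.6/0.3/0.1 | 11–28% over all settings | (same range) |
| Background mix 0.4/0.4/0.2 | 1.5–3% over all settings | (same range) |

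The last row is the nominal error rate, since a two-sided 5% test gives 2.5% in each direction.

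**Other measures, all added events rated 1.**
- *Event count, t-test:* the arm with added events is significantly worse in 96% to 100% of trials at background 1 and about 81% to 99% at background 2, and better in none.
- *Sum of severity ratings, 0 if no event:* significantly worse in 34% to 95%. In a separate set of scenarios (50 or 75 per arm), Mann-Whitney on this sum favoured the arm with added events in at most 0.1% of trials.
- *Worst severity, 0 if no event:* significantly worse in only 3% to 36%; favours the arm with added events in no more than about 2%.
- *Per-event mean with event-free patients set to 0:* still favours the arm with added events in about 1% at background 1, but in 19% to 44% at background 2. Adding a zero rule to the mean is therefore not a reliable cure.

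**The case against.** Four points can be made for the plan.

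1. **The wording leaves the denominator open.** With weekly collection, the mean could be taken over weeks, with 0 for event-free weeks. Every patient would then have a value and the reversal would disappear. This stands as a limit: the per-event mean is the more natural reading of the sentence, but neither it nor the exclusion of event-free patients is a stated rule.

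2. **The large percentages need every added event to carry the lowest rating.** This stands. The effect shrinks with a milder mix and vanishes when added events resemble the background. Nothing in the SAP says which pattern to expect.

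3. **The same sentence tests the sum.** Read as a count, it detects the extra events. A reader might infer from the severity result that the trial's safety conclusion as a whole would reverse. The document does not support that, because the sum by t-test and the post-treatment incidence are also compared. What remains is that two significant results can point in opposite directions with no rule for reading them together. Average severity per event is a legitimate description, but a test of it is not a test of harm.

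4. **The post-treatment comparison concerns a severity rating, not a stated mean.** A reader might carry the dilution argument over to it. The text does not show that. Only the missing value for event-free patients applies there.

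**Conclusion.** The point holds for the severity comparison over the treatment period. On the plain per-event reading, the chosen summary can move in the opposite direction to harm, and it is undefined for patients without an event. Under the assumed rates, ratings and arm sizes, the arm with added events is falsely favoured in about 55% to 98% of trials in the extreme case where all added events have the lowest rating, in 11% to 28% when they are moderately milder, and at the nominal rate when they have the same mix. The fault is in the summary and its unstated denominator, not in the Mann-Whitney test.

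This is worth changing before analysis. It concerns one safety comparison and not the primary outcome.

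**What to change.** - Replace the per-patient mean with a score that exists for every randomised patient with adverse-event reports: the sum of severity ratings over the treatment period, 0 if no event, compared by Mann-Whitney. Report worst severity (0 if no event) alongside.
- State whether the sum already in the sentence is a count of events or a sum of ratings, so that the two are not confused.
- Score the post-treatment severity rating 0 for patients who report no event.
- Give mean severity per event descriptively only, next to the event count.

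The cost is a reworded sentence or two and a recoded variable from data already collected. The sum mixes frequency with severity, so it cannot separate one severe event from several mild ones; worst severity complements it there but has little power against added mild events. A sum also depends on how many weekly reports a patient returned, so the number of reports per arm should be shown beside it.
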